14. STUDY MONITORING

The trial will be conducted in accordance with the current approved protocol, ICH GCP, relevant regulations, and standard operating procedures.

The Sponsor's designees will monitor all aspects of the study carefully with respect to ICH GCPs and SOPs for compliance with applicable government regulations. The investigator is responsible for providing all study records, including eCRFs, source documents, etc., for review and inspection by the clinical monitor.

eCRF will be periodically monitored and source verified against corresponding source documentation (e.g., office and clinical laboratory records) for each subject. Clinical monitors will evaluate periodically the progress of the study, including the verification of appropriate consent form procedures, review of drug accountability and study drug preparation procedures, adherence to dosing procedures, the investigator's adherence to the protocol, maintenance of records and reports, review of source documents for accuracy, completeness, and legibility, and review of study regulatory documents, including, but not limited to: study agreement, study insurance, study approval letters by the IRB/IEC and the Regulatory Authority, site staff CV and financial statements, study forms, protocol signature page, etc. In addition, the monitor shall review completed eCRF and study documentation for accuracy and completeness, and protocol compliance. The monitor should assure that data captured in the eCRF is fully supported by the source documents. Clinical monitors will also ensure that all protocol requirements, applicable Food and Drug Administration (FDA) regulations (CFR Title 21 Parts 50, 56, and 312 and ICH Guidelines for GCP - E6), other requirements, and Investigator's obligations are being fulfilled.

By signing this protocol, the Investigator grants permission to the Sponsor (or designee), and appropriate regulatory authorities to conduct on-site monitoring and/or auditing of all appropriate study documentation.

Apart from assuming responsibility for the communication between the investigator and the Sponsor, the clinical monitor duties include:

- On-site visits; and
- · Review of study documents and results.

On-site monitoring visits include pre-study/qualification visits, initiation visits, interim monitoring visits, and a close-out visit at the end of the study. At the close of the study, the monitor will be required to make a final on-site visit to assure that all study data has been properly completed.

Reports of on-site visits shall be made by the monitor and should include, as applicable, resolution of concerns and queries, completion of appropriate follow-up activities, completion of assigned tasks, and corrective actions. Monitoring visit follow-up letters will be sent to the site for filing and adherence.

All data generated in the current clinical investigation will be managed according to relevant guidelines (e.g. GCP, 21 CFR Part 11).

15. ETHICAL AND REGULATORY CONSIDERATIONS

15.1. Declaration of Helsinki

This study will be conducted in accordance with the ethical principles that have their origin in the Declaration of Helsinki and that are consistent with the Good Clinical Practice and the applicable regulatory requirements.

15.2. ICH Guidelines for Good Clinical Practice

The Investigator will ensure that this trial is conducted in full conformity with relevant regulations and with the ICH Guidelines for Good Clinical Practice (CPMP/ICH/135/95) July 1996.

15.3. Approvals, Information on Study Infants, and Consent Form

This trial will be initiated only after all required legal documentation has been reviewed and approved by the respective IRB / Independent Ethics Committee (IEC) and competent authority (CA) according to national and international regulations. The same applies for the implementation of changes introduced by amendments. Prior to an infant's participation in the trial, written informed consent must be obtained for each infant (by both parents and accepted legal representatives) according to ICH GCP and the regulatory and legal requirements of the participating country. Each signature must be personally dated by each signatory, and the informed consent form and any additional infant information form must be retained by the investigator as part of the trial records. A signed copy of the informed consent form and any additional infant information must be given to each infant's parents or the infant's legally accepted representative.

The parents must be informed that his/her personal trial-related data will be used by Nutrinia in accordance with the local data protection law. The level of disclosure must also be explained to the parents.

15.4. Data Quality Assurance

A quality assurance audit/inspection of this trial may be conducted by the sponsor or sponsor's designees or by IRBs/IECs or by regulatory authorities. The quality assurance auditor will have access to all medical records, the investigator's trial-related files and correspondence, and the informed consent documentation of this clinical trial.

15.5. Participant Confidentiality, data disclosure and publication

Subject medical information obtained as a result of this study is considered confidential. Disclosure to third parties other than those noted below is prohibited. All reports and communications relating to subjects and their parent(s) or guardians(s) in this study will identify all persons only by their initials and number. Medical information resulting from a subject's participation in this study may be given to the subject's personal physician or to the appropriate medical personnel responsible for the subject's welfare. Data generated as a result of this study are to be available for inspection on request by FDA or

other government regulatory agency auditors, the Sponsor, the Sponsor-assigned clinical monitor (or designee), and the IRB/IEC.

All laboratory specimens, evaluation forms, reports, and other records that leave the site will be identified by a coded number to maintain subject confidentiality. All records will be maintained in lockable file cabinets. All computer entry and networking programs will be identifiable only by coded numbers. Clinical information will not be released without written permission from the subject's parent or guardian, except as necessary for monitoring by the IRB, the FDA, or representatives of the study Sponsor.

Any information, inventions, or discoveries (whether patentable or not), innovations, suggestions, ideas, and reports, made or developed by an investigator as a result of conducting this study shall be promptly disclosed to the Sponsor and shall be the sole property of the Sponsor. The Investigator agrees, upon the Sponsor's request and at the Sponsor's expense, to execute such documents and to take such other actions, as the Sponsor deems necessary or appropriate, to obtain patents in the Sponsor's name covering any of the foregoing.

The results of this study will be published under the direction of the Sponsor. Results will not be published without prior review and approval by the Sponsor.

15.6. Expenses and Benefits

No complications are anticipated from feeding the infant with the study insulin-enriched oral nutrition. No evidence or scientific findings of long-term negative effects stemming from feeding preterm infants with the insulin-enriched nutrition have been noted. This is also true when administering higher concentrations of insulin than the quantity proposed in this trial. Nonetheless, the possibility of long-term effects on the creation of insulin antibodies or the prevention of diabetes cannot be ruled out. A study infant may experience a slight but insignificant drop in the blood sugar level.

Should the trial show that insulin indeed speeds up the maturation of the digestive tract, a study infant treated with NTRA-2112 may reach full nutrition sooner than would have occurred had the infant not been in the trial. This would reduce the risks to preterm infants and may provide better growth and development. In addition, the infant will contribute to study a new medication that may help thousands of pre-term infants born each year and suffer from complications due to immature digestive system Nutrinia is responsible for managing the financing for the study. Nutrinia has signed a contract with the facilities where they will perform the trial with the study doctor. The participation of the infant in the study will not involve any costs and the infant's parent or guardian will not have to pay for the study drugs.

16. RETENTION OF STUDY DOCUMENTS

The PI should retain records for all study infants, including eCRFs, all source documentation (containing evidence of study eligibility, history and physical findings, laboratory data, results of consultations, etc.) as well as IRB/IEC records and other regulatory documentation in a secure storage facility. The records should be accessible for inspection and copying by authorized authorities.

Essential documents must be retained for a minimum of 2 years after the final marketing approval in an ICH region or at least 2 years have elapsed since the discontinuation of clinical development of the investigational product. In addition, all medical records of the infant and other source documentation will be kept for the maximum time permitted by the hospital, institution, or medical practice.

17. FINANCE AND INSURANCE

17.1. Funding

Financing of this study will be outlined in a separate document.

17.2. Insurance

Insurance of this study will be outlined in a separate document.

The terms and conditions of the insurance cover are made available to the investigator and the parents through documentation in the Investigator Site File.

18. PUBLICATION POLICY

The investigator contract describes the rights of the investigator and of the sponsor with regard to publication of the results of this trial. As a general rule, no trial results should be published prior to finalization of the Clinical Trial Report to regulatory authorities.

The Principal Investigator will prepare a complete review of the study and abstracts for professional meetings. Published data must not compromise the objectives of the study or the confidentiality of the infants enrolled.

[figure not shown]

Appendix B: Study Flow Diagram

Appendix C: SAE Reporting Flow Chart

AE: Adverse event

[figure not shown]
SAE: Serious adverse event

SAR: Serious adverse reaction

[figure not shown]
SUSAR: Suspected unexpected serious adverse event

Appendix D: Fenton Preterm Growth Chart

Appendix E: Expected Complications Related to Premature Birth

While not all premature babies experience complications, being born too early can cause short-term and long-term health problems for preemies. Generally, the earlier a baby is born, the higher the risk of complications. Birth weight plays an important role, too.

Some problems may be apparent at birth, while others may not develop until later.

Short-term complications

In the first weeks, the complications of premature birth may include:

- Breathing problems. A premature baby may have trouble breathing due to an immature respiratory system. If the baby's lungs lack surfactant a substance that allows the lungs to expand he or she may develop respiratory distress syndrome because the lungs can't expand and contract normally.
 - Preemies may also develop chronic lung disease known as bronchopulmonary dysplasia. In addition, some preemies experience prolonged pauses in their breathing, known as apnea.
- Heart problems. The most common heart problems premature babies experience are patent ductus
 arteriosus (PDA) and low blood pressure (hypotension). PDA is a persistent opening between two major
 blood vessels leading from the heart.
 - While this heart defect often closes on its own, left untreated it can cause too much blood to flow through the heart and cause heart failure as well as other complications. Low blood pressure may require adjustments in intravenous fluids, medicines and sometimes blood transfusions.
- Brain problems. The earlier a baby is born, the greater the risk of bleeding in the brain, known as an
 intraventricular hemorrhage. Most hemorrhages are mild and resolve with little short-term impact. But
 some babies may have larger brain bleeding which causes permanent brain injury.
 - Larger brain bleeds may lead to fluid accumulation in the brain (hydrocephalus) over a number of weeks. Some babies who develop hydrocephalus will require an operation to relieve the fluid accumulation.
- Temperature control problems. Premature babies can lose body heat rapidly; they do nott have the stored body fat of a full-term infant and they cannot generate enough heat to counteract what's lost through the surface of their bodies. If body temperature dips too low, hypothermia can result.
 - Hypothermia in a preemie can lead to breathing problems and low blood sugar levels. In addition, a preemie may use up all of the energy gained from feedings just to stay warm, not to grow bigger. That is why smaller preemies require additional heat from a warmer or an incubator until they are larger and able to maintain body temperature without assistance.
- Gastrointestinal problems. Preemies are more likely to have immature gastrointestinal systems, leaving
 them predisposed to complications such as necrotizing enterocolitis (NEC). This potentially serious
 condition, in which the cells lining the bowel wall are injured, can occur in premature babies after they
 start feeding. Premature babies who receive only breast milk have a much lower risk of developing NEC.
- Blood problems. Preemies are at risk of blood problems such as anemia and infant jaundice. Anemia is a common condition in which the body does not have enough red blood cells. While all newborns experience

a slow drop in red blood cell count during the first months of life, the decrease may be greater in preemies, especially if the baby has a lot of blood taken for lab tests.

Infant jaundice is a yellow discoloration in a newborn baby's skin and eyes that occurs because the baby's blood contains an excess of a yellow-colored pigment from the liver or red blood cells (bilirubin).

- Metabolism problems. Premature babies often have problems with their metabolism. Some preemies
 may develop an abnormally low level of blood sugar (hypoglycemia). This can happen because preemies
 typically have smaller stores of glycogen (stored glucose) than do full-term babies and because preemies'
 immature livers have trouble converting stored glycogen into glucose.
- Immune system problems. An underdeveloped immune system, common in premature babies, can lead
 to infection. Infection in a premature baby can quickly spread to the bloodstream causing sepsis, a
 lifethreatening complication.

Long-term complications

In the long term, premature birth may lead to these complications:

- Cerebral palsy. Cerebral palsy is a disorder of movement, muscle tone or posture that can be caused by
 infection, inadequate blood flow or injury to a preemie's developing brain either during pregnancy or while
 the baby is still young and immature.
- Impaired cognitive skills. Premature babies are more likely to lag behind their full-term counterparts on various developmental milestones. Upon school age, a child who was born prematurely might be more likely to have learning disabilities.
- Vision problems. Premature infants may develop retinopathy of prematurity, a disease that occurs when
 blood vessels swell and overgrow in the light-sensitive layer of nerves at the back of the eye (retina).
 Sometimes the abnormal retinal vessels gradually scar the retina, pulling it out of position. When the
 retina is pulled away from the back of the eye, it is called retinal detachment, a condition that, if
 undetected, can impair vision and cause blindness.
- Hearing problems. Premature babies are at increased risk of some degree of hearing loss. All babies will have their hearing checked before going home.
- Dental problems. Preemies who have been critically ill are at increased risk of developing dental problems, such as delayed tooth eruption, tooth discoloration and improperly aligned teeth.
- Behavioral and psychological problems. Children who experienced premature birth may be more likely
 than full-term infants to have certain behavioral or psychological problems, such as
 attentiondeficit/hyperactivity disorder (ADHD). However, more recent research suggests that at least
 for late preterm babies the risk of ADHD may be the same as it is for children who were born at full
 term.
- Chronic health issues. Premature babies are more likely to have chronic health issues some of which
 may require hospital care than are full-term infants. Infections, asthma and feeding problems are more
 likely to develop or persist. Premature infants are also at increased risk of sudden infant death syndrome
 (SIDS).

Appendix F: Example for TBV volume

TBV is considered based on the following table:

Subjects Weight (Kg)	Total Blood Volume (mL)	Maximum in 24 hours (3 mL/kg)	Maximum in 30 day period (5% of TBV)
1	100	3	5
2	200	6	10
3	240	9	12
4	320	12	16
5	400	15	20
6	480	18	24
7	560	21	28
8	640	24	32
9	720	27	36
10	800	30	40
11-15	880-1200	33-45	44-60
16-20	1280-1600	48-60	64-80

Statistical Analysis Plan V1.3 SAP Date: 06APR2018

NCT02510560

Statistical Analysis Plan

A Multi-center, Double-blind, Randomized, Three-Arm, Parallel-Group, Placebo Controlled Study to Assess the Efficacy and Safety of NTRA-2112 on Intestinal Malabsorption in Preterm Infants

PROTOCOL NO. FIT-04

Version 7.0 10 May 2017

Sponsor: Nutrinia Ltd

[name] Israel

CRO:

[figure not shown]
Version: 1.3

Date: 06-Apr-2018

Confidential Page 1 of 40

Statistical Analysis Plan V1.3 SAP Date: 06APR2018

SIGNATURE PAGE

APPROVED BY:

Approver

Name

Title

Sponsor Company

Signature Date:

Approver

Name

Title

Signature **Sponsor Company** Date:

Page 2 of 40 Confidential

DOCUMENT REVISION HISTORY

VERSION	DATE	AUTHOR/ UPDATED BY	COMMENTS
V1.0	03-July-2017		
V1.1	27-Sept- 2017		Revision after receiving FDA comments on V1.0 dated 3 July 2017
V1.2	11-Feb-2018		The reporting periods for AE reporting have been further defined in Section 2.3.2.1. Changed the hypothesis testing
			procedure for primary and key secondary endpoints.
			Re-calculated the sample size due to the testing procedure. The timing of sample size restimation relative to the futility analysis is further clarified. Added a clarification for the average scores to be used for tied observations in SAS one-way nonparametric procedure.
			added a sensitivity analysis using the baseline enteral feeding volume to break the tied NFE ranking.
			added a summary for number and percent of infants who achieve the complete and partial enteral feeding success for each treatment.

Confidential Page 3 of 40

		Section 2.2.1.3.2 was modified to allow longer time, up to 180 days, to observe the actual time for discharge or being ready to be discharged.
V1.3	06APR2018	Section 3.1 Changed the conditional power from 20% to 35%. Based on the conditional power and the totality of the clinical data available at the futility analysis, the DMC will recommend to continue or discontinue one or both dose arms. Section 3.1 Added language that the sponsor will consider increasing the total sample size up to 450 patients based on the sample size re-estimation.

Confidential Page 4 of 40

TABLE OF CONTENTS

1	INTRO	DUCTION	9
1.1 Study Objectives		9	
	1.1.1	Primary Objective	9
	1.1.2	Secondary Objective	
	1.1.3	Safety Objective	
	_	DY ENDPOINTS	
	1.2.1	Primary Efficacy Endpoint	
	1.2.2	Secondary Efficacy Endpoints	
	1.2.2	, 	
	1.2.2		
	1.2.3	Exploratory Secondary Efficacy Endpoints	

	6.1 PART	IAL DATES FOR ADVERSE EVENTS AND PRIOR/CONCOMITANT MEDICATION	3938

ABBREVIATIONS

Abbreviation	Term	
AE	Adverse event	
ANCOVA	Analysis of Covariance	
ATC	Anatomical Therapeutic Chemical Classification System	
CRF	Case Report Form	
CI	Confidence Interval	
СТ	Clinical trials	
CTCAE	Common Terminology Criteria for Adverse Events	
DMC	Data Monitoring Committee	
eCRF	Electronic Case Report Form	
EN	Enteral nutrition	
EOT	End of Treatment	
FAS	Full Analysis Set	
FEF	Full Enteral Feeding	
GA	Gestational Age	
ICF	Informed Consent Form	
MAR	Missing at Random	
MedDRA	Medical Dictionary for Regulatory Activities	
ND	Not done	
NEC	Necrotizing enterocolitis	
NFE	Number of days to full enteral feeding	
NGT	Nasogastric tube	
NICU	Neonatal intensive care unit	
NRD	Number of days to discharge from the hospital	
OGT	Orogastric tube	
OGTT	Oral glucose tolerance test	
OMM	Own mothers milk	
PDA	Patent ductus arteriosus	
PE	Physical examination	
PI	Principal Investigator	
PN	Parenteral nutrition	
PP	Per protocol	
PT	Preferred Term	
SAE	Serious adverse event	
SAP	Statistical Analysis Plan	
SD	Standard Deviation	
SOC	System Organ Class	
TEAE	Treatment Emergent Adverse Event	
SAR	Serious Adverse Reaction	
SUSAR	Suspected unexpected serious adverse reaction	

Confidential Page 7 of 40

Statistical Analysis Plan V1.3 SAP Date: 06APR2018

Abbreviation	Term
TBV	Total Blood Volume
TMF	Trial Master File
TPN	Total parenteral nutrition
WHO	World Health Organization

Confidential Page 8 of 40

Statistical Analysis Plan V1.3 SAP Date: 06APR2018

1 INTRODUCTION

The purpose of this statistical analysis plan (SAP) is to describe the procedures and the statistical methods that will be used to analyze and report results for Protocol FIT-04.

1.1 STUDY OBJECTIVES

1.1.1 Primary Objective

To assess the efficacy of 2 doses of NTRA-2112 as compared to placebo on intestinal malabsorption in preterm infants as measured by the time to full enteral feeding.

Achievement of enteral feeding will be regarded as the first of 3 consecutive days consumption of at least 150 ml/kg/day enteral feeding (EN).

The three treatment groups are

- Placebo
- NTRA 2112 400 (μIU Insulin/ml)
- NTRA 2112 2000 (μIU Insulin/ml)

1.1.2 Secondary Objective

Key secondary objective:

To assess the effect of 2 doses of NTRA-2112 compared to placebo on the number of days to achieve discharge from hospital or readiness for discharge, whichever occurs first.

Readiness for discharge from hospital is defined as achieving all of the below:

- Infant weight $\geq 1800g$
- Stable body temperature

Capable of oral feeding (reached full enteral feeding and not dependent on parenteral nutrition [PN]).

Other secondary objectives:

To compare 2 doses of NTRA-2112 to placebo with respect to the following:

- Growth parameters (g/kg/day) at 6, 8, and 10 days, the last day of treatment (or Day 28), day of discharge, 3-month corrected follow-up, 12-month corrected follow-up, and 24-month corrected follow up
- Change in Z-score at 6, 8, and 10 days, the last day of treatment (or Day 28), day of discharge, 3-month corrected follow-up, 12-month corrected follow-up, and 24-month corrected follow up

Confidential Page 9 of 40

• Gain in body weight at 6, 8, and 10 days, the last day of treatment (or Day 28), day of discharge, 3-month corrected follow-up, 12-month corrected follow-up, and 24-month corrected follow up

- Number and percentage of infants reaching full enteral feeding within 6, 8, and 10 days from initiation of treatment
- Total number of days receiving parenteral nutrition
- Number of days to 120Kcal/kg/day
- Number of days to wean-off PN (Wean off PN is defined as complete cessation of PN support.)

Exploratory secondary objective:

• Number of days to end gastric residuals over 2 ml/measurement according to the feeding protocol.

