1.6.5 Missing Data Handling Rules

The primary approach to handling missing ranks for the primary and the key secondary endpoints will be multiple imputation. The details are provided in Section 2.2.1.3.

No imputation will be made for other secondary or exploratory endpoints. No imputation will be made for any safety or lab measurements.

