2.2.2 Other Secondary Endpoints

The following other secondary endpoints will be analyzed on FAS only.

- Growth velocity (g/kg/day) at 6, 8, and 10 days, the last day of treatment (or Day 28), day of discharge, 3-month follow-up, 12-month follow-up, and 24-month follow up
- Change in Z-score at 6, 8 and 10 days, the last day of treatment (or Day 28), day of discharge, 3-month follow-up, 12-month follow-up, and 24-month follow up from initiation of treatment
- Gain in body weight at 6, 8, and 10 days, the last day of treatment (or Day 28), day of discharge, 3-month follow-up, 12-month follow-up, and 24-month follow up

Confidential Page 27 of 40

• Number and percentage of infants reaching full enteral feeding within 6, 8, and 10 days from initiation of treatment.

- Total number of days receiving parenteral nutrition
- Number of days to 120Kcal/kg/day
- Number of days to wean-off PN

For the continuous variables (growth velocity, z-score, body weight), ANCOVA analysis will be performed at each time point of interest, including treatment, the stratification factors of gestation age and region (North America, Europe, and Israel) as class variables, and the baseline values as a continuous covariate, the estimated treatment differences (NTRA-2112 minus placebo), 95% confidence intervals, and P-values will be provided.

For the variable of number of day to a given event, the van Elteren test stratified for gestation age and region will be performed. The average score will be used for the ties. Infants who experience NEC (Necrotizing Enterocolitis) and infants who die will be assigned the second worst and the worst ranks. The individual ranks among subjects experiencing NEC and the individual ranks among subjects who die will be handled according to Section 1.3.3.

For percent of infants reaching full external feeding, Cochran-Mantel-Haenszel (CMH) test stratified for gestation age and region will be performed.

Statistical testing of these other secondary endpoints will be considered exploratory and will not control for Type I error rate inflation.

No imputation will be performed for the missing values for the other secondary endpoints.

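### Growth at 3, 12 and 24 months is tested visit by visit on whoever is observed, so loss that depends on growth after baseline and differs between arms would bias these exploratory estimates

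*SAP*

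**What the plan says.** SAP 1.1.2 and 1.2.2.2 list growth velocity, change in Z-score and weight gain at eight times: Days 6, 8 and 10, end of treatment, discharge, and 3, 12 and 24 months. The Z-score entry in SAP 1.1.2 opens with "Change in Z-score at 6, 8, and 10 days, the last day of treatment (or Day 28), day of discharge, 3-month corrected follow-up"; the two later visits complete it.

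The analysis is in SAP 2.2.2: "For the continuous variables (growth velocity, z-score, body weight), ANCOVA analysis will be performed at each time point of interest". Gestational-age group and region enter as class factors beside treatment, "and the baseline values as a continuous covariate". Treatment differences, 95% confidence intervals and P-values are reported.

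On missing values, SAP 2.2.2 says "No imputation will be performed for the missing values for the other secondary endpoints", and SAP 1.6.5 says the same in general terms: "No imputation will be made for other secondary or exploratory endpoints". SAP 1.6.4 leaves a follow-up visit missing when its window holds no observation. The missing-data sensitivity analyses in SAP 2.2.1.4 cover only the primary and key secondary endpoints.

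SAP 2.2.2 labels these growth tests exploratory, without Type I error control. Protocol 12.4.7 planned only descriptive summaries at 12 and 24 months. Under Protocol 12.4 the SAP prevails where the two differ.

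**The concern.** An infant weighed at Days 6, 8 and 10 and at 3 months, but not at 24 months, counts at the earlier times and adds nothing to the 24-month comparison. Yet those earlier weights are likely to predict the 24-month weight, and may also predict who is lost. The per-visit model cannot use them because baseline is its only growth covariate.

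If slow growers are lost more often from one arm, the infants still observed there look better grown, and the ANCOVA reports part of that as a treatment difference. The 12- and 24-month visits are the most exposed.

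The documents contain two possible routes to such loss, without showing that either will operate. Protocol 9.5.1 ends follow-up for withdrawals after Day 28 caused by an event judged unrelated to the product, so loss can follow health. SAP section 2 unblinds the study once the last infant has completed the 3-month visit and does not say whether sites and families stay blinded for later visits.

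**Working it through.** **The plan's own figures.** There is no sample size, SD or loss rate for growth. The only attrition allowances concern the primary endpoint: (130 − 115)/130 = 11.5% in SAP 1.3.3, and 5% in SAP 3.1 (144/0.95 = 151.6, stated as 152). Neither describes loss by 24 months, so a range of 10–30% is used.

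**Assumptions.** 130 infants per arm (SAP 1.3.3), no true drug effect, outcome SD 1, two-sided 5% test. Gestational-age and region strata are left out for simplicity. Two simulation settings:

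- *Setting A*, 1,500 trials per scenario. The 24-month Z-score correlates 0.35 with baseline, 0.65 with 3 months and 0.80 with 12 months. Loss depends on the 3-month Z-score with log-odds −0.7 per SD.
- *Setting B*, 2,000 trials per scenario. The 24-month correlation is 0.25–0.45 with baseline and 0.70–0.90 with 12 months. Loss depends on the latest weight with log-odds ±1 per SD.

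**When bias appears (Setting B, planned ANCOVA at 24 months).**

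| Loss pattern | Bias (SD) | Error rate |
|---|---|---|
| Random, 20% in both arms | 0.00 | 4.4–5.2% |
| Random, 10% v 30% | within 0.005 | 4.7–5.4% |
| Lighter infants lost, same rule, 20% in both arms | within 0.004 | 5.1–5.7% |
| Lighter infants lost, 10% placebo v 30% active | +0.09 to +0.10 | 10.7–12.6% |
| 20% in both arms, weight-related in placebo only | −0.09 to −0.11 | 9.9–14.0% |

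Both conditions are needed: dependence on growth after baseline, and a difference between arms in rate or in kind.

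**Size of the bias (absolute value, SD).**

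| Loss | One arm only, −0.7 | One arm only, −1 | Opposite directions, 0.7 | Opposite directions, 1 |
|---|---|---|---|---|
| 10% | 0.03–0.04 | not run | 0.07 | about 0.10 |
| 20% | 0.06–0.07 | 0.09–0.11 | 0.13 | 0.19–0.21 |
| 30% | 0.09–0.10 | not run | 0.19 | 0.28–0.32 |

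Opposite-direction loss gives about twice the one-arm bias. Halving the last column therefore suggests about 0.05 SD at 10% and 0.14–0.16 SD at 30% for one-arm loss at log-odds −1.

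**Check by hand (one arm, −0.7).** Let p be the loss probability. The mean 3-month Z-score of the infants kept shifts by s = 0.7 × E[p(1−p)]/(1 − loss), where E[p(1−p)] ≈ v − (0.7v)² and v = loss × (1 − loss). With an assumed baseline-to-3-month correlation of 0.5, the ANCOVA bias is about (0.65 − 0.35 × 0.5) × s = 0.475s.

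- 10%: v = 0.09, E = 0.086, s = 0.067, bias 0.03
- 20%: v = 0.16, E = 0.147, s = 0.129, bias 0.06
- 30%: v = 0.21, E = 0.188, s = 0.188, bias 0.09

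These match the lower ends of the simulated ranges.

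**Using the earlier weights.** A likelihood analysis (A) kept bias below 0.01 SD. Multiple imputation from all earlier weights (B) kept it within 0.006 SD, with error rates of 4.2–5.9%. Part of this is by construction, since loss was generated from observed weights.

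**Precision under random loss (Setting A).** Ratio of standard errors, planned ANCOVA to longitudinal analysis: 0.124/0.121 = 1.02 at 10%, 0.131/0.124 = 1.06 at 20%, 0.141/0.129 = 1.09 at 30%.

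**The case against.** The strongest reply is that nothing confirmatory rests here. The growth tests lie outside the four-step hierarchy of SAP 1.7. Three measures at eight times for two doses make 3 × 8 × 2 = 48 unadjusted tests, so a raised error rate in one of them breaks no guarantee the SAP gives. That stands, and it sets the priority.

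Second, in a double-blind trial with no drug effect, loss has little reason to depend on growth differently by arm. This also stands in part: the two routes noted above make such loss possible, not established. At 10% loss in one arm only (log-odds −0.7) the error rate is 6%. The Monte Carlo standard error with 1,500 runs is 0.56 points, so that is barely distinguishable from 5%.

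Third, a repeated-measures model has its own weaknesses. It assumes data missing at random given the observed weights. A reader might take that as strictly weaker than what the ANCOVA needs, but it is not: the ANCOVA tolerates growth-related loss that is equal in both arms, even when it depends on growth nobody recorded. The model also extrapolates weights for infants who died, and Day 28 is not a common time because treatment stops at an earlier discharge. The simulations used fewer visits than the model proposed below. These points shape the fix and do not remove the reason for it.

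Finally, the SAP turned the Protocol's descriptive 12- and 24-month summaries into tests without listing this in its section 4. Returning to description would remove the P-values, but the arm summaries would still rest on whoever was observed.

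**Conclusion.** The point holds in a limited form. The 3-, 12- and 24-month growth comparisons use only infants observed at each visit, adjust for no growth after baseline and have no missing-data check. Bias follows if loss depends on growth after baseline and also differs between arms. With loss tied to growth in one arm only, it is about 0.03–0.04 SD at 10% loss and 0.09–0.10 SD at 30% (log-odds −0.7), and 0.06–0.11 SD at 20% across log-odds −0.7 to −1. Stronger dependence or opposite directions by arm would raise it. The precision cost under random loss is about 2–9% in standard error. All loss rates, correlations and dependence strengths are assumptions.

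Two stronger readings are not supported. A reader might infer that uneven loss by itself creates a false treatment difference; random loss of 10% v 30% gave none, and the documents give no follow-up loss rate or pattern from which to predict more. A reader might also infer that only completers are analysed and earlier weights discarded; in fact an infant missed at 12 months still counts at 24, and each weight enters the analysis of its own visit. In-hospital times are much less exposed, because infants are assessed daily.

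**What to change.** In SAP 2.2.2, for weight Z-score and body weight:

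1. Add one likelihood-based repeated-measures model over Days 6, 8 and 10 and 3, 12 and 24 months, with treatment-by-visit and baseline-by-visit terms, gestational-age group, region and unstructured covariance.
2. Report the 3-, 12- and 24-month treatment differences from this model, and keep the per-visit ANCOVA as supportive.
3. Leave the end-of-treatment and discharge times as separate ANCOVAs, because their timing varies by infant.
4. Report deaths by arm beside the model, and do not treat weights after death as ordinary missing data.
5. State the missing-at-random assumption, and that it differs from the assumption behind the per-visit ANCOVA.

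The cost is SAP wording and one extra model on data already collected. Six visits give 6 × 7/2 = 21 covariance parameters, which about 390 infants should support.
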